 1. non injurious behaviors: facial expressions, non-aggressive vocalizations (mumbling, gentle talking, casual conversation, singing, laughing...), twitches, gentle shaking, non-aggressive movements of fingers, arms or legs...;

2. potentially injurious: punching, kicking, arm flailing or thrashing around, at least one limb or head out of bed, sitting up in bed, crawling, attempting to stand up or leave bed, near falls, cursing, screaming, shouting, yelling, or any behavior requiring bed partner to wake up participant;
 3. injurious: any contact with bed partner (hitting or grabbing), wall or furniture, any fall or leaving bed (doving out, walking, jumping).
- CGI efficacy scale (CGE-E): 4-point therapeutic effect scale and 4-point side effect scale, jointly filled by patient and partner on last day of treatment
 - CGI improvement scale (CGI-I): 7-point improvement scale filled by clinician on last day of treatment
 - RWAi according SINBAR criteria comparing PSG pre-intervention to PSG post-intervention
 - video-PSG analysis of REM related vocalizations and movements (“simple” versus “complex”) as per Sixel-Döring and colleagues¹⁶
 - Sleep outcomes: EDS, Karolinska 1 h after awakening

Exploratory Endpoints

- “Activity index” as recorded by actigraphy¹⁷ (percentage of 30-second epochs with an activity score above zero) last month of treatment compared to 1-month baseline
- Sleep outcomes: PSQI
- Cognitive outcome: MoCA
- Mood and Anxiety: PHQ-9 and GAD-7
- Orthostatic vital signs

Sample Size Justification/Statistical Analysis

Sample size calculation was made for the outcome of number of RBD episodes per month. Based on the data published by Brunetti et al.¹⁸, the number of RBD episodes decreased from 11.2 \pm 5.2 at baseline to 10.3 \pm 3.7 per month in the placebo arm. To detect an effect size of 50% reduction in the number of RBD episodes per month ([placebo-active]/placebo) with a power of 80% and alpha of 5%, the number of participants would need to be 10 per arm. Based on prior studies using SXB in subjects with PD, a conservative drop out rate of 15-20% could be anticipated^{14,15}, which would require to enroll at least 24 participants, i.e. 12 participants per arm.

Reporting to Jazz Pharmaceuticals

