Sodium Oxybate in Treatment-Resistant REM Sleep Behavior Disorder (RBD): A Randomized Placebo-Controlled Trial

Statistical Analysis Plan

NCT04006925

January 11, 2023

Statistical analysis (using SAS 9.4, Cary, NC) was by intention-to-treat for the primary efficacy analysis, comparison of baseline characteristics, safety and tolerance and per-protocol (PP) for secondary/exploratory analyses. PP analysis included all participants who completed titration and the 4-week treatment period. Sample size calculation was based on a prior randomized controlled study by Brunetti et al.²⁵ To detect an effect size of 50% reduction in the number of RBD episodes per month ([placebo - active] / placebo) with a power of 80% and alpha of 5%, the number of participants needed to be 10 per arm. Anticipating a dropout rate of 20%, 24 participants required to be enrolled.

We tested the primary hypothesis that SXB is superior to placebo in reducing the number of RBD episodes from baseline, as observed in the last month of treatment using linear mixed effects models with random intercepts. Models were parameterized in two ways to estimate separate group trajectories and between-group differences in change over time. Cohen's d was calculated as a measure of treatment effect size. Similar hypotheses were tested on secondary and exploratory outcomes. Within- and between-group differences were assessed with paired- and unpaired t-tests, or with the Wilcoxon Signed Rank and Mann-Whitney U tests for nonnormal data. Bootstrapped percentile-based 95% confidence intervals were calculated based on 10,000 randomly resampled datasets. Participants scoring below 4 on the CGI-I and CGI-E were classified as "responders"; chi-square tests were performed to compare the proportion of responders between groups. All statistical tests were conducted using a 2-sided alpha level of 0.05. For secondary/exploratory analyses, bootstrapped percentile-based 95% confidence intervals were calculated based on 10,000 randomly resampled datasets. Descriptive statistics on safety data are provided for all randomized participants (intention-to-treat), by treatment group and study phase.

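### At the SAP's 20% dropout, 24 enrolled leaves about 19 completers, not the 20 it calls for; 24 covers dropout only up to 16.7%

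*SAP*

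**What the plan says.** The SAP's opening paragraph sets the base size: "with a power of 80% and alpha of 5%, the number of participants needed to be 10 per arm". The effect to be detected is a 50% reduction in monthly RBD episodes relative to placebo. The next sentence moves from that base to enrolment: "Anticipating a dropout rate of 20%, 24 participants required to be enrolled".

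The protocol (Sample Size Justification/Statistical Analysis) has the same base of 10 per arm but a range for attrition: "a conservative drop out rate of 15-20% could be anticipated", "which would require to enroll at least 24 participants, i.e. 12 participants per arm". It cites a placebo arm from a published trial with 10.3 episodes per month (SD 3.7) at follow-up and 11.2 (SD 5.2) at baseline.

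Neither document gives the formula used to go from 10 to 12 per arm.

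**The concern.** An allowance for dropout is meant to leave the required number once the expected losses have occurred. The SAP gives the number required (20), the expected loss (20%) and the number enrolled (24), so a reader can check the statement directly, and it does not hold. The protocol's figure depends on which end of its own range is used.

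At stake are the accuracy of the sample-size statement and whether the shortfall takes power for the primary comparison below the stated 80%.

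**Working it through.** **Inputs**
- Required per arm: 10, so 20 in total (SAP and protocol).
- Enrolled: 24, 12 per arm (protocol; the SAP gives the total).
- Dropout: 20% (SAP); 15-20% (protocol).
- Power 80% and alpha 5% (both documents). Two-sided is taken from the SAP's general rule: "All statistical tests were conducted using a 2-sided alpha level of 0.05".
- Difference: 50% of the placebo mean, 0.5 × 10.3 = 5.15 episodes per month.
- SD: 3.7, the placebo follow-up value. This is an assumption, because the documents do not say which SD was used for planning.

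**Step 1. Reproduce the base size.** For a two-sample comparison of means, the normal approximation gives n = 2(1.96 + 0.84)² × 3.7² / 5.15² ≈ 8.1, rounded up to 9 per arm. The exact t-test calculation (noncentral t) gives 79.2% power at 9 per arm and 83.7% at 10, so 10 is the smallest size reaching 80%. The stated 10 per arm is reproduced.

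**Step 2. Check the enrolment figure.** Completers = enrolled × (1 − dropout). Required enrolment = 20 / (1 − dropout).

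| Dropout | Completers from 24 | Per arm | Enrolment needed for 20 |
|---|---|---|---|
| 15% | 20.4 | 10.2 | 23.5, so 24 |
| 16.7% | 20.0 | 10.0 | 24 |
| 20% | 19.2 | 9.6 | 25 (26 with equal arms, since 10/0.8 = 12.5 rounds up to 13) |

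The limit for 24 is 1 − 20/24 = 16.7%. The SAP's 20% lies above it; the protocol's range straddles it.

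**Step 3. Where 24 could come from.** 20 × (1 + 0.20) = 24 exactly, which is a common slip. But 20/0.85 = 23.5, which also rounds up to 24 by the correct formula at the protocol's lower rate. The documents do not show which route was taken.

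**Step 4. Effect on power** (t-test, two-sided 5%, difference 5.15, SD 3.7):

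| Completers per arm | Power |
|---|---|
| 10 and 10 | 83.7% |
| 9.6 and 9.6 (expected number) | 82.0% |
| 9 and 10 | 81.5% |
| 9 and 9 | 79.2% |
| 12 enrolled per arm, averaged over random 20% dropout (binomial) | 81.1% |

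**Step 5. Sensitivity to the assumed SD.** The largest SD at which 10 per arm still gives 80% power is about 3.89. At that value, 9.6 per arm gives 78.2%. At the baseline SD of 5.2, 10 per arm gives only 55% power and the calculation would need 18 per arm, so 5.2 does not reproduce the plan's figure.

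**The case against.** The best defence is that nothing of substance is lost. The gap is 0.4 of a participant per arm, and power stays above the 80% target. The primary analysis is intention-to-treat with a mixed model, so a participant who leaves is not automatically lost from it. The protocol's wording is a floor with a range, and 24 is right at 15%. Its Scientific Basis/Rationale section also reports 10% dropout due to side effects in the two earlier Parkinson's disease studies, and at 10% the number left would be 24 × 0.9 = 21.6.

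Most of this stands, and it is why the point is minor. It does not make the SAP's statement correct: the SAP names 20% alone and pairs it with 24. The mixed model softens the loss but does not remove it, since the primary endpoint is the last month of treatment, which early leavers may not supply.

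A reader might go further in three ways that the documents do not support:
- *That the sponsor multiplied by 1.2 instead of dividing by 0.8.* The match is exact, but no formula is given and a correct route at 15% also gives 24. This remains an inference.
- *That the trial is underpowered because of this error.* Under the inputs that reproduce 10 per arm, it is not.
- *That the per-protocol secondary and exploratory analyses fall short of a required 10 per arm.* The protocol says the calculation was made for the number of RBD episodes per month, the primary endpoint. Neither document sets a size or power for the other outcomes.

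**Conclusion.** The point holds as an arithmetic inconsistency of minor consequence. On the SAP's own figures, 24 enrolled leaves 19.2 expected completers at 20% dropout, against 20 required. The shortfall in enrolment is one participant, or two with equal arms. The protocol's figure is correct for the lower part of its range, up to 16.7%, and not for the rest.

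Expected power for the primary comparison falls from 83.7% with 10 completers per arm to about 81-82%. That remains above 80% because 10, the next whole number, carried some slack. This rests on a difference of 5.15, an SD of 3.7, a two-sided t-test and the loss of every dropout from the analysis. The inconsistency itself needs none of these assumptions. If the planning SD was nearer 3.89, expected power would be about 78%, still a small change.

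**What to change.** No extra enrolment is needed. Replace the SAP's enrolment sentence with one that agrees with its own figures, for example:

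> Enrolling 24 participants retains 10 per arm at dropout of up to about 16.7%. At 20% dropout about 19 are expected to complete (9 to 10 per arm), giving about 81% power for a difference of 5.15 episodes per month, assuming an SD of 3.7 and a two-sided alpha of 0.05.

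If the sponsor's calculation used a different SD, state that value and recompute the power. In the protocol's sample size section, note that 24 covers the lower part of the 15-20% range only, up to about 16.7%.

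The cost is one sentence in each document and a slightly less favourable statement. Conduct and analysis do not change.

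### The CGI responder rule of below 4 leaves the CGI-E part and coding unstated, and with about 10 per arm the dichotomised comparison can lose substantial power against a rank test

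*SAP*

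**What the plan says.** The SAP gives a single rule: "Participants scoring below 4 on the CGI-I and CGI-E were classified as" responders. It adds that "chi-square tests were performed to compare the proportion of responders between groups". The protocol (Secondary Endpoints) describes the CGI-I as a "7-point improvement scale filled by clinician on last day of treatment" and the CGI-E as a "4-point therapeutic effect scale and 4-point side effect scale, jointly filled by patient and partner on last day of treatment".

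Neither document gives the numeric codes, the direction of scoring, the CGI-E part to which the rule applies, or a way of combining the two parts. No expected responder rate or power is stated for the CGI.

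The SAP analyses secondary outcomes "per-protocol (PP) for secondary/exploratory analyses", so the CGI comparison uses completers. It also provides for Mann-Whitney U tests where data are not normal, but the only analysis it names specifically for the CGI is the responder chi-square. It does not say which CGI analysis is the main one.

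**The concern.** Global impression is the first item under Secondary Objectives in the protocol. One numeric cut on scales of different length raises two problems.

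- **Definition.** An analyst cannot apply the rule to the CGI-E from the text alone, because the answer depends on the coding and on the part used.
- **Information.** On a 4-point scale coded 1 to 4, the rule keeps only the split between the category scored 4 and the other three. If many placebo patients fall below 4, both arms sit near the ceiling. With about 10 per arm, a real difference could then go undetected although the full scores would show it.

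**Working it through.** **1. The plan's own figure, to fix n and a reference effect.** The SAP says "with a power of 80% and alpha of 5%, the number of participants needed to be 10 per arm". This is for monthly RBD episodes. The protocol (Sample Size Justification/Statistical Analysis) gives a placebo follow-up mean of 10.3 and SD of 3.7, with a 50% reduction to detect.
- Difference: 0.5 × 10.3 = 5.15.
- Normal approximation: n = 2 × (1.96 + 0.84)² × (3.7/5.15)² ≈ 8.1, so 9 per arm. The t-test version needs 10 per arm (power 0.837). The stated 10 is reproduced.
- Completers from 12 per arm: 12 × 0.85 = 10.2 and 12 × 0.80 = 9.6, so about 10.
- Standardised effect: 5.15/3.7 = 1.39 SD. Nothing in the documents links this to a CGI rating; it serves only as a reference.

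**2. What below 4 covers.**
- CGI-I coded 1 to 7: three of seven categories.
- A CGI-E part coded 1 to 4, with 1 best: three of four.
- A CGI-E part coded 1 to 4, with 4 best: also three of four, but the best outcome is the one excluded.
- A CGI-E part coded 0 to 3: all four, so everyone is a responder and power is zero.
- A score combining both parts: no rule is given.

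**3. A ceiling check that needs no effect model.** Suppose all 10 active patients respond. The uncorrected chi-square is 20 × (10 × 4)²/(10 × 10 × 16 × 4) = 5.00 (p = 0.025) with 6 placebo responders, and 20 × (10 × 3)²/(10 × 10 × 17 × 3) = 3.53 (p = 0.060) with 7. Significance therefore needs at most 6 placebo responders, and power is P(Bin(10, q) ≤ 6), where q is the placebo responder rate:
- q = 50%: 83%
- q = 60%: 62%
- q = 75%: 22%
- q = 80%: 12%

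**4. The split against the rank test.** Assumptions: 1 to 4 coding with 1 best, 10 per arm, two-sided 0.05 ("All statistical tests were conducted using a 2-sided alpha level of 0.05"), and a latent normal shift of 1.39 SD. A cumulative placebo proportion q becomes Φ(Φ⁻¹(q) + 1.39) on active. For q = 0.60 this is Φ(0.253 + 1.39) = 0.95. Chi-square power is the sum of binomial probabilities over all tables with p ≤ 0.05. Mann-Whitney power is simulated, with an error of about two points.

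| Placebo %, best to worst | Placebo below 4 | Active below 4 | Chi-square, below 4 | Chi-square, best two | Mann-Whitney |
|---|---|---|---|---|---|
| 20/30/35/15 | 85% | 99% | 5% | 52% | 74% |
| 25/25/25/25 | 75% | 98% | 19% | 52% | 72% |
| 10/20/40/30 | 70% | 97% | 28% | 64% | 77% |
| 10/20/30/40 | 60% | 95% | 43% | 64% | 76% |
| 5/15/30/50 | 50% | 92% | 52% | 64% | 77% |
| 3/7/20/70 | 30% | 81% | 64% | 55% | 75% |
| 2/3/10/85 | 15% | 64% | 61% | 42% | 67% |

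Simulating the chi-square as well gives the same picture within about two points: 20 to 54% against 73 to 78% for placebo response of 50 to 75%, and 61 to 63% against 68 to 75% for the last two rows.

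**5. Smaller effect.** At a shift of 1.0 SD over the same seven distributions, the below-4 chi-square has about 4 to 39% power and Mann-Whitney about 36 to 50%. Mann-Whitney is ahead in every row. The smallest gain is about 3 points, in the last row. Its type I error was at or below 5%.

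These calculations are for a 4-category scale. No separate power figure was computed for the CGI-I.

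**The case against.** The strongest case on the other side has five parts.

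- **The rule may be coherent.** If 4 on the CGI-I means no change and the worst therapeutic-effect category means no effect, below 4 means any improvement on both scales. This stands as a possible reading, though the documents do not state it.
- **A large loss of power is not a given.** A reader might infer that the rule necessarily costs much power. It does so only if placebo response is moderate or high. Low placebo response is quite compatible with the documents: participants are refractory, and the planning data show placebo moving only from 11.2 to 10.3 episodes per month. This stands.
- **A stricter cut is not the cure.** A reader might infer that the best two categories should define response. With placebo 3/7/20/70% that cut has 55% power against 64% for below 4. At a shift of 0.8 SD with placebo 5/15/30/50%, the two cuts are about equal (22% and 24%). This stands.
- **The side-effect part.** A reader might infer that patients are called responders on their side-effect score. The SAP does not say so; it only leaves the part unspecified.
- **The rank test is already in the SAP.** True, as a general provision for nonnormal data. But the SAP does not assign it to the CGI, and the responder chi-square is the one test it does assign. This reduces the change to one of definition and priority.

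The analysis is also secondary, per-protocol and unpowered by design, which limits its importance.

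**Conclusion.** The point holds in a limited form. The SAP does not say which CGI-E part or coding its responder rule uses. The three-of-four count is therefore conditional on 1 to 4 coding, and 0 to 3 coding would make the rule empty.

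Under 1 to 4 coding with 1 best, the rule may be a lenient but consistent any-improvement definition. Even then, the chi-square gives up about 25 to 53 points of power to Mann-Whitney when 50 to 75% of placebo patients score below 4 (77 − 52 and 72 − 19). It gives up about 6 to 11 points when 15 to 30% do (67 − 61 and 75 − 64).

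The sizes rest on assumed placebo distributions and on a 1.39 SD shift borrowed from the episode count. The direction was the same in every distribution and at both shifts tested. The documents do not support saying that power is lost heavily whatever the placebo response, or that the two responder labels must differ in meaning. The primary endpoint and its sample size are untouched.

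**What to change.** - Make the between-group Mann-Whitney comparison of the CGI-I score, and of the CGI-E therapeutic-effect score, the main CGI analysis.
- Report the CGI-E side-effect part under tolerability.
- Keep the responder rate as supportive. For the CGI-E, define it on the therapeutic-effect part only, and state the codes, the direction and what below 4 means on each scale.
- Do not require a stricter cut. The SAP is dated January 2023 and written in the past tense; if results were already known, label any new cut as post hoc and disclose the change of priority.

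The cost is SAP wording and a rerun on scores already collected. The downside is that the headline becomes a rank comparison rather than a simple percentage; the supportive responder rate partly makes up for this.

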- In individuals without a diagnosis of Parkinson's disease (PD), PSG-confirmed “definite RBD” per the International Classification of Sleep Disorders, 3rd edition (ICSD-3)
- In individuals with a diagnosis of PD, either PSG-confirmed diagnosis of RBD ("definite RBD") or history of dream-enactment ("probable RBD")
- RBD episodes ≥ 2 /week or ≥ 8 /month (defined as vocalization and/or limb or body movements attributed to dream-enactment)
- Reliable reporting by bed witness in the absence of patient awareness

Exclusion Criteria

- History of falls during ambulation in the last 6 months despite adequate neurologic treatment
- Requirement of an ambulatory device at home
- Inadequately treated symptomatic orthostatic hypotension (syncopal episode in the last 6 months)
- BMI > 35
- Untreated or uncontrolled OSA (4% desaturation AHI>15)
- Liver impairment
- Renal impairment
- Congestive heart failure
- Uncontrolled hypertension
- Treatment with valproic acid
- Current history of NREM parasomnias or parasomnia overlap syndrome (at least 2 episodes in the last 6 months)
- Diagnosis of narcolepsy
- Cognitive impairment resulting in inability to comply with treatment instructions
- Diagnosis of any dementia including dementia with Lewy bodies
- Diagnosis of multiple system atrophy
- RBD attributed to a CNS lesion
- PD Hoehn and Yahr stage 4 and 5
- Any change of PD regimen during the study period
- Current alcoholism or prior history of drug abuse
- Pregnancy
- Epilepsy currently treated with sedating antiepileptic drugs;
- Concomitant use of other CNS depressants, including but not limited to opioid analgesics, benzodiazepines other than clonazepam, muscle relaxants, and/or illicit CNS depressants
- Current depression (at least PHQ-9 score = 10), history of psychosis
- Any change of antidepressant regimen during the study period
- Chronic severe RLS (iRLS>20) (at least 3 days per week)
- Succinic semi-aldehyde dehydrogenase deficiency (SSADH)

Primary Endpoint

- Number of RBD episodes in one month (RBD log), last month of treatment compared to 1-month baseline

Secondary Endpoints

- Severity of RBD episodes in one month (RBD log), last month of treatment compared to 1-month baseline. Severity is scored from 1 to 3 (1: least severe, 3 most severe):

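### Percentile-bootstrap intervals labelled 95% cover about 92-93% between arms and 90-91% within arms if they are for means, at 10 to 12 completers per arm

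*SAP*

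**What the plan says.** The SAP is a short text without numbered sections. On intervals for the secondary and exploratory outcomes it says: "For secondary/exploratory analyses, bootstrapped percentile-based 95% confidence intervals were calculated based on 10,000 randomly resampled datasets". Earlier in the same paragraph almost the same sentence appears without that restriction: "Bootstrapped percentile-based 95% confidence intervals were calculated based on 10,000 randomly resampled datasets". Neither sentence says what is bootstrapped (mean, mean difference, median, Cohen's d or model coefficient), whether resampling is done separately by arm, or whether a corrected form such as BCa or bootstrap-t is used. The protocol does not mention the bootstrap.

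The tests that these intervals accompany are given as: "Within- and between-group differences were assessed with paired- and unpaired t-tests, or with the Wilcoxon Signed Rank and Mann-Whitney U tests for nonnormal data". The test level is also fixed: "All statistical tests were conducted using a 2-sided alpha level of 0.05".

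Secondary and exploratory analyses are per-protocol, and that set is defined as follows: "PP analysis included all participants who completed titration and the 4-week treatment period". On numbers, the SAP requires 10 per arm and adds: "Anticipating a dropout rate of 20%, 24 participants required to be enrolled". The protocol's sample-size section splits the 24 as 12 per arm.

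**The concern.** For a mean, the percentile bootstrap has no small-sample correction. The bootstrap variance uses the divisor n instead of n-1, and the limits sit at roughly normal quantiles instead of t quantiles. Both make the interval too short, and both matter at about 10 per arm. More resamples remove Monte Carlo noise only.

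What is at stake is reading. The same paragraph sets its tests at 5% and labels its intervals 95%, yet an interval for a mean would have an error rate of about 7-8% between arms and 9-10% within an arm. An interval could exclude zero beside a t-test that is not significant. In a trial this small, the secondary results will be read largely through their intervals.

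The unrestricted sentence also leaves it unclear whether the interval for the primary outcome is a percentile bootstrap. That may be no more than a drafting repetition.

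**Working it through.** **Inputs.** Nominal level 95%, percentile method and 10,000 resamples (SAP). Two-sided alpha 0.05 (SAP). 12 enrolled per arm (protocol, sample-size section) and 20% dropout (SAP): 12 × 0.8 = 9.6, so about 10 completers. The actual number of completers is not given, so n = 8 is added as a sensitivity case.

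**The plan's own n.** With the cited placebo mean of 10.3 and SD 3.7 (protocol, sample-size section), a 50% reduction is 0.5 × 10.3 = 5.15 episodes. A two-sample t calculation at 80% power and two-sided 5% gives 9.17, that is 10 per arm, as stated. Ten to twelve per arm is therefore the right range for the check.

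**Coverage for a mean, normal data.** The percentile limits are approximately x̄ ± 1.96 · s · √((n-1)/n) / √n. Hence

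coverage = P(|t_df| < c), with c = 1.96 · √((n-1)/n), df = 2n-2 between arms and df = n-1 within an arm.

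The width relative to the t interval is c / t_(0.975, df). The largest t-test p-value at which the interval can still exclude zero is 1 - coverage.

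| n per arm | c | Coverage between / within | Width ratio between / within | Largest p between / within |
|---|---|---|---|---|
| 8 | 1.833 | 91.2% / 89.1% | 0.855 / 0.775 | 0.088 / 0.109 |
| 10 | 1.859 | 92.1% / 90.4% | 0.885 / 0.822 | 0.079 / 0.096 |
| 12 | 1.877 | 92.6% / 91.3% | 0.905 / 0.853 | 0.074 / 0.087 |

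**Simulation check, normal data.** With 10,000 resamples and 3,000 trials (Monte Carlo SE about 0.5 points), coverage was 92.0% and 92.3% between arms and 91.1% and 91.4% within, for n = 10 and n = 12. In a second simulation (1,000 resamples, 4,000 trials), t intervals covered 94.8-95.6%.

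**Other readings of the SAP** (second simulation, n = 10 and 12).
- Resampling not stratified by arm, normal data: 93.0-93.1% between arms.
- Heavy-tailed data (t with 5 df): 90.9-92.3% between, 89.9-90.8% within.
- Exponential data: 90.4-91.2% between, 86-87% within.
- Medians: 96-97% between, 93-94% within. The between-arm shortfall disappears.

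**Does the normality screen remove the problem?** The SAP sends nonnormal data to rank tests but does not say how normality was judged. A Shapiro-Wilk screen (p ≥ 0.05 in both arms) was assumed, with 4,000 trials and 2,000 resamples. Between-arm coverage among outcomes that passed, n = 10 then n = 12:

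| Data shape (assumed) | Percentile | t interval |
|---|---|---|
| Normal | 91.6%, 92.4% | 94.7%, 95.4% |
| Integer scores, SD 3 | 92.2%, 91.8% | 94.6%, 94.2% |
| Integer scores, SD 1.5 | 94.3%, 93.9% | 96.0%, 95.7% |
| Gamma, shape 4 | 90.9%, 91.9% | 94.8%, 94.6% |
| Exponential | 87.5%, 87.5% | 92.0%, 91.8% |

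**How often interval and t-test would disagree.** With no true effect, the between-arm rate per endpoint is 0.95 - coverage: 0.0294 at n = 10 and 0.0239 at n = 12. The protocol lists 11 secondary and exploratory endpoints apart from the CGI scales, which go to a responder test: RBD severity, RWAi, video-PSG, the sleepiness scale, Karolinska, activity index, PSQI, MoCA, PHQ-9, GAD-7 and orthostatic vital signs. If all 11 were analysed as means, the expected number of disagreements is 11 × 0.0294 = 0.32 or 11 × 0.0239 = 0.26. The chance of at least one, for inter-endpoint correlations of 0 and 0.5 (assumed; 20,000 simulated trials), is 28% and 25% at n = 10, and 23% and 22% at n = 12. If only 5 of the 11 went to t-tests (illustrative), it is 13-14% or 11%.

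**The case against.** The strongest reply is that the SAP never says that means were bootstrapped. Rank tests stand in the same sentence as the t-tests, and for a difference in medians the between-arm problem vanishes. This stands as a limit on the claim, and the figures above apply to means only. But a t-test compares means, so an interval for a mean is the natural companion of every outcome tested that way.

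The between-arm figure also depends on choices that the SAP leaves open. It is 92.6% at n = 12, about 93% if resampling is not stratified by arm, and about 94% for coarse integer scores. All remain below 95%, and stratification does not affect the within-arm intervals.

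Treating all 11 endpoints as means is an upper bound. Severity, for instance, is scored 1 to 3 per episode ("Severity of RBD episodes in one month (RBD log), last month of treatment compared to 1-month baseline"), and questionnaire scores such as those under "Mood and Anxiety: PHQ-9 and GAD-7" may be skewed enough to go to rank tests. The documents do not show how many would, so the 22-28% is a ceiling and not a forecast.

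The consequence is small: no p-value, primary test or decision rule changes. In context the unrestricted bootstrap sentence most likely belongs to the secondary outcomes, since it follows the statement about them. The t interval is not perfect either, covering about 92% between arms for screened exponential data. Finally, the SAP is written in the past tense, so a new interval method would be a change after analysis and should be declared as one. All of this supports a minor grading; none of it makes the percentile interval for a mean a 95% interval at this sample size.

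**Conclusion.** The concern holds, as a minor point. For secondary and exploratory outcomes reported as means, with roughly normal data and 10 to 12 completers per arm, the intervals fall short of their label by about 2 to 3 percentage points between arms and 4 to 5 within an arm. Such an interval can exclude zero while the t-test gives p between 0.05 and about 0.08 (between arms) or 0.10 (within an arm). Under the null, a between-arm disagreement somewhere in the trial is possible but not likely.

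The conclusion rests on the statistic being a mean or mean difference, which the SAP suggests but does not state, and on the number of completers being near plan. Fewer completers or skewed data make the shortfall larger; coarse integer scores make it smaller. Whether the primary interval is affected cannot be settled from the text.

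**What to change.** - For outcomes analysed by t-test or mixed model, replace the percentile interval with the t or model-based interval with small-sample degrees of freedom. Bootstrap-t is an option where a mean of clearly skewed data is reported.
- For rank-tested outcomes, name the location estimate and give an interval for it. An interval from inverting the Mann-Whitney test covered 95.5-95.8% in untied simulated data but 98-99% in integer scores, so note that ties make it conservative.
- If any bootstrap interval is kept, state the statistic and whether resampling is by arm.
- Delete the unrestricted bootstrap sentence, or limit it, so that the method for the primary interval is clear.
- Record the date of the change and that it followed the analysis, if it did.

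The cost is SAP wording and a re-run of the secondary and exploratory intervals from existing data. Intervals for means widen by about 10-13% between arms (1/0.905 to 1/0.885) and 17-22% within an arm (1/0.853 to 1/0.822). Under strong skew the t interval is an improvement but not a full repair.
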